9.3 POPULATIONS FOR ANALYSES

For the efficacy analysis, we will utilize a modified ITT population. Participants will be part of the modified ITT population as defined by the following criteria:

1. Randomized to NDURE or Usual Care
2. Receipt of curative intent surgery at MUSC
3. Indication for PORT (with or without concurrent chemotherapy) per NCCN Guidelines based on the presence of at least one of the following adverse features on final pathologic evaluation: ENE, positive margin, pT3 or pT4 primary, at least pN1 nodal disease (per AJCC 8th edition for p16-ve

non-oropharyngeal SCC or AJCC 7th edition for p16+ve oropharyngeal SCC), nodal disease in levels IV or V, PNI or LVI

The modified ITT analytic population addresses the fact that eligibility, registration, randomization, and delivery of a portion of the intervention (NDURE or Usual Care) occur prior to definitive treatment of the HNSCC. However, the primary study objective (and endpoint) are defined and evaluable only for patients who undergo surgery for HNSCC and have an indication for adjuvant therapy (which can only be definitively known following surgical resection). Therefore, we expect that a predictable subset of patients will be enrolled in the study, based on meeting all inclusion, be randomized to NDURE or Usual Care, receive a portion of the intervention (NDURE Visit 1) and then subsequently develop a study exclusion criterion based on interval information that becomes available later in the clinical course that cannot be known at the time of study enrollment and registration, namely:

- failure to undergo curative intent surgery at MUSC (exclusion criteria #4)
- lack of indication for PORT (with or without chemotherapy) per NCCN Guidelines (exclusion criteria #5)

As such, patients who meet study inclusion criteria but subsequently develop exclusion criteria #4 or #5 during the course of the study will be replaced since the primary endpoint is anchored to findings that occur after analysis of the pathologic specimen obtained during surgery. Patients in the modified ITT population for whom the primary endpoint is not evaluable due to loss to follow-up will be considered navigation failures, and their time to PORT will be treated as exceeding 6 weeks for the purposes of analysis.

We will also perform an efficacy analysis on the per-protocol analytic dataset, a subset of the modified ITT population who completed all 3 NDURE study sessions. These patients are judged to have complied with the protocol sufficiently to ensure that these data would be likely to represent the effects of the NDURE intervention according to the underlying scientific model.

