3 OBJECTIVES AND ENDPOINTS

Table 1. Study Objectives and Endpoints

OBJECTIVES	ENDPOINTS
NDURE FEASIBILITY STUDY	
Primary	
To assess the feasibility of NDURE among white and AA HNSCC patients.	NDURE Accrual Rate NDURE Completion Rate NDURE Session Completion Rate Questionnaire Completion Rate
Secondary	
To assess the acceptability of NDURE to white and AA HNSCC patients and HNSCC providers.	Patient Satisfaction with the Interpersonal Relationship with the Navigator Scale Score Patient Satisfaction with Logistical Aspects of Navigation Scale Score
To determine the feasibility of a single dedicated navigator to manage a caseload of patients for the NDURE intervention	Navigator Caseload Navigator Time Allocation (Direct) Navigator Time Allocation (Indirect)
To evaluate the feasibility of collecting pre- and post-NDURE intervention outcome measures in this patient population	Study questionnaire completion rate
RCT of NDURE VERSUS USUAL CARE	
Primary	
To evaluate the preliminary clinical impact of NDURE compared with UC on delays starting PORT among white and AA HNSCC patients.	PORT Delay Time-to-PORT (TTP) Initiation
Secondary	
To evaluate the preliminary clinical impact of NDURE compared with UC on racial disparities in delays starting PORT among white and AA HNSCC	PORT Delay TTP Initiation

Table 1. Study Objectives and Endpoints

OBJECTIVES	ENDPOINTS
patients.	
To assess the preliminary clinical impact of NDURE compared with UC on barriers to care	Barriers Resolution Rate Unresolved barriers
To determine the preliminary clinical impact of NDURE compared with UC on cancer care delivery processes	Pre-surgical Radiation Consultation Pre-RT Dental Extractions Surgery to Pathology Report \leq 7 d Surgery to PORT Referral \leq 10 d RT Referral to Consult \leq 10 d RT Consult to Initiation \leq 21 d
To evaluate the preliminary behavioral mechanism of action of NDURE	Care Transition Measure-15 (CTM-15) Score Change from Baseline in Interpersonal Support Evaluation List-12 Scale Score Change from Baseline in Perceived Susceptibility Scale Scores Change from Baseline in Illness Perception Questionnaire-Revised (IPQ-R) Consequences Sub-Scale Score Change in Baseline from Perceived Barriers Scale Change in Baseline from Communication & Attitudinal Self-Efficacy Scale (CASE)-Cancer Score

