4.2.3.2 JUSTIFICATION FOR NUMBER, FREQUENCY, AND TIMING OF INTERVENTION CONTACTS

The three NDURE sessions, which are expected to take 30-60 minutes each, will coincide with the presurgical consult, hospital discharge, and 1st postoperative clinic visit. These time points were chosen to facilitate case identification (preoperatively; Visit 2) and coordination across key care transitions from inpatient to outpatient status at the time of hospital discharge (inpatient; Visit 3) and from surgical to radiation and medical oncology specialties (post-discharge; Visit 4). These timepoints also promote the feasibility of NDURE delivery as nearly 100% of patients attend these three visits (despite travel distance-related barriers⁴¹) since patients 1) cannot have surgery without their presurgical consult; 2) are hospitalized postoperatively; and 3) return for the 1st postoperative visit for drain/tube removal. The number of intervention contacts is justified by the need to focus the intervention to key transitions of care as described above.

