As a result of the aforementioned three strategies, retention of subjects is expected to be highly feasible. The scheduled timepoints of navigator-participant interaction (initial surgical consultation, prior to hospital discharge, first clinic visit after hospital discharge) were chosen because these are situations in which the likelihood of contact is ~100%. Although challenges with retention for cancer studies due to mortality (overall and disease-specific) and treatment toxicity are potentially problematic, we do not think that they will limit retention in this feasibility study of NDURE. The rate of on-treatment mortality (during surgery or adjuvant therapy) is quite low (<5%) and the study follow-up does not extend past the completion of therapy. Thus, lack of retention due to mortality is not expected to be significant. Treatment toxicity is potentially a problem, as patients may not want to answer surveys while undergoing treatment or choose to withdraw due to competing treatment demands. We do not expect this to be a problem, however, because NDURE will be integrated into routine clinical care and thus should not create an excess time burden for patients. In fact, it is likely that participation in the intervention, which is expected to improve care coordination and decrease barriers to care, will make this potential source of dropout less likely than other intervention trials. Using NDURE to address individualized barriers to timely HNSCC treatment is a significant strength and innovation of the study and will likely also improve retention relative to historical rates.

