6.1.2.2 USUAL CARE

UC consists of discussions about the indications, risks/benefits/alternative, Guidelines, timing, and logistical details of adjuvant therapy. These discussions will be administered according to practice patterns of the involved providers. As such, usual care is expected to be variable in the number, frequency, intensity, and duration of visits and discussions dedicated to planning adjuvant therapy, depending upon the patient, provider, caregiver, tumor board, and clinical scenario. Usual care will be delivered in the following settings: the MUSC Head and Neck Tumor Center and MUSC hospital. No dedicated interventionist will deliver usual care; instead a combination of physicians (attendings and residents), nurse practitioners, and nurses from the relevant multidisciplinary specialties (surgical,

medical, radiation oncology) at MUSC or an outside facility will all contribute to these discussions. Administration of usual care will consist of direct face-to-face communication and other methods (e.g. telephone call, e-mail correspondence). The face-to-face conversations can occur during a structured clinical setting (e.g. clinic visit) or more informal, non-appointment-based manner (e.g. inpatient rounds). Given the variability in expected delivery of usual care, there is no number of sessions that constitute “full-dose”. Because the administration schedule and dose of usual care is highly variable, usual care will not be dose-matched to NDURE on intensity, duration, and/or frequency. However, the three clinical encounters at which NDURE will be delivered are clinical in nature and thus will likely correlate highly with usual care. Participants in the trial are permitted to interact with other participants after randomization, regardless of treatment allocation. Such encounters may occur in waiting rooms before or after clinic appointments given the single-site design of the trial.

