6.4 STUDY INTERVENTION/EXPERIMENTAL MANIPULATION ADHERENCE

Participants’ adherence with study procedures will be tracked by attendance at intervention visits. All study visits are mandatory to remain an active participant. Adherence to attendance at Visits 2-4 will be ascertained from the NDURE visit note authored by the navigator that is available in the EMR. Adherence to attendance at Visits 1 and 5 will be ascertained from the REDCap data collection form. Adherence to attendance at visits 1-5 will be documented in the electronic Case Report Form (eCRF).

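### The barriers-versus-usual-care objective has no stated usual-care data source or between-arm test, and the per-protocol efficacy set has no usual-care rule

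*Combined protocol and SAP*

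**What the plan says.** **Per-protocol set.** Section 9.3 defines the modified ITT population for efficacy and then undertakes to "perform an efficacy analysis on the per-protocol analytic dataset", described as "a subset of the modified ITT population who completed all 3 NDURE study sessions". It names no comparator. For usual care, section 6.1.2.2 says "Given the variability in expected delivery of usual care, there is no number of sessions that constitute" a full dose, and also "No dedicated interventionist will deliver usual care". Section 6.4 says "Adherence to attendance at Visits 2-4 will be ascertained from the NDURE visit note authored by the navigator", and adds that attendance at all five visits is entered in the eCRF.

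**Barriers.** Section 3 sets the secondary objective "To assess the preliminary clinical impact of NDURE compared with UC on barriers to care", with barrier resolution rate and unresolved barriers as its endpoints. Section 8.1 takes both from the navigator log during the NDURE intervention, and describes the log as counting barriers in the barrier reduction plan during NDURE. Section 9.4.3.2 summarises both at the end of NDURE, then models PORT delay on unresolved barriers by logistic regression, adjusting for the covariates of section 8.1. The between-arm tests come in the next paragraph and are assigned to the other secondary endpoints. The section closes by placing all secondary endpoints on the modified ITT population.

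**The concern.** Two analyses presented as efficacy or between-arm results lack a defined control side.

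For the per-protocol set, completing navigator sessions is something only NDURE patients can do in the literal sense. If the analyst fills the gap with all usual-care patients, the NDURE arm is filtered on post-randomization behaviour and the control arm is not. The plan's own rules could link that filter to the outcome. Under section 7.3 a patient who misses two visits and cannot be reached is lost, and under section 9.3 a lost patient without an evaluable endpoint counts as delayed. Such patients could drop out of the completer set together with their imputed delays, while their usual-care counterparts would stay in. With no rule stated, the comparator could also be chosen after the data are seen.

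For barriers, a stated secondary objective of the RCT would have endpoint data defined for one arm only and no named test. The regression attached to it would adjust for a data-collection inventory instead of a chosen set.

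**Working it through.** **1. The plan's own figure.** Inputs from section 9.2.2: 75 per arm, 45% versus 25%, two-sided alpha 0.10. Pooled rate 0.35. Null SE = √(2×0.35×0.65/75) = 0.0779. Alternative SE = √((0.45×0.55 + 0.25×0.75)/75) = 0.0762. Power = Φ((0.20 − 1.645×0.0779)/0.0762) = 82.7%, against the stated 83%. It reproduces, and nothing below changes it.

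**2. Per-protocol bias if completers are compared with all 75 usual-care patients.** Let p be the NDURE-arm delay rate, c the share completing three sessions and d the delay rate in non-completers. Completers' delay = (p − (1−c)d)/c. With no true effect, p = 0.45. For c, section 4.2.3.2 expects that "nearly 100% of patients attend these three visits", and section 5.5 says "these are situations in which the likelihood of contact is ~100"%; I use 95-98%. The documents do not give d, so 70-90% is an assumption. Rejection rates are exact enumerations of the unstratified pooled z test at two-sided 0.10.

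| c (completers) | d | completers' delay | false benefit (points) | rejection favouring NDURE | total rejection |
|---|---|---|---|---|---|
| 98% (74) | 70% | 44.5% | 0.5 | 5.6% | 10.0% |
| 98% (74) | 90% | 44.1% | 0.9 | 6.1% | 10.1% |
| 95% (71) | 70% | 43.7% | 1.3 | 7.1% | 10.4% |
| 95% (71) | 90% | 42.6% | 2.4 | 9.0% | 11.4% |

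For example, (0.45 − 0.05×0.90)/0.95 = 0.426. With no selection (d = 45%) the false benefit is zero for any c, and rejection favouring NDURE is 4.9-5.2%. With d = 60% the false benefit is 0.3-0.8 points. At the two-sided 0.05 level of section 9.4.1, total rejection for the four rows runs from 4.9% to 6.2%.

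A pessimistic c of 85% (64 completers) gives 4.4-7.9 points and 13-25% rejection favouring NDURE at 0.10, for the same d. That 85% is the feasibility threshold among enrolled patients in section 9.2.1, not a modified ITT figure.

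**3. Barriers, section against section.**
- Objective (section 3): NDURE against usual care.
- Endpoint source (section 8.1): navigator log, during NDURE.
- Timing of summary (section 9.4.3.2): end of NDURE.
- Usual-care recorder: none named; section 6.1.2.2 provides no dedicated interventionist.
- Between-arm test: none named for these two endpoints.

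The Perceived Barriers Questionnaire is self-reported, scheduled at Visits 1, 3, 4 and 5, and covered by the planned rank sum comparison of change scores. Section 3 assigns it to the mechanism objective, not to this one.

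**4. Barrier regression.** Items under Covariates in section 8.1: 11 demographic + 7 tobacco and alcohol + 12 clinical and oncologic + 3 cultural subscales + 1 nomogram = 34. One of them is treatment dates; the surgery and PORT dates determine the outcome.
- NDURE only: 75×0.25 = 18.75 to 75×0.45 = 33.75 events; divided by 34, 0.6-1.0 per item.
- Both arms: 33.75 + 18.75 = 52.5 (planned effect) to 2×33.75 = 67.5 (no effect) events; divided by 34, 1.5-2.0 per item.

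**The case against.** **The control arm may not be empty.** Section 6.4 makes all visits mandatory for participants without an arm limit and records attendance at Visits 1-5 in the eCRF. The schedule in section 1.3 has a joint NDURE/usual-care row at Visits 2-4, and section 6.1.2.2 expects the three encounters to overlap heavily with usual care. The protocol also uses the name NDURE loosely for the trial. So the sessions could be read as Visits 2-4 in either arm. This stands as far as it goes: a reader might infer that no usual-care patient could ever qualify, but that is the literal reading and not a certainty. What remains is that section 9.3 specifies NDURE sessions, gives no usual-care rule, and the only attendance source named for those visits is the navigator's note.

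**The bias is small.** This also stands. It needs a comparison that the plan does not state and an assumed d, and the analysis is additional to modified ITT.

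**Usual care may be logged.** The schedule's title covers both arms and lists the barrier log without an arm split, including at Visits 1 and 5, outside the navigation sessions. Section 9.4.3.2 places all secondary endpoints on modified ITT, which holds both arms. A reader might therefore take the regression to be NDURE-only by design; the documents do not settle that. But the same schedule lists navigator caseload and satisfaction with the navigator, which cannot apply to usual care, so it does not establish usual-care logging. An analysis population is not a data source. Even if the generic tests were read to cover barriers, the control data would still be unspecified.

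**Conclusion.** The point holds as a specification gap in one supportive efficacy analysis and one secondary objective. The primary modified ITT comparison and the 83% power are untouched.

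The barriers gap is the more important. As written, the comparison with usual care cannot be answered on its own two endpoints, because neither a usual-care source for the log nor a between-arm test is given.

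The per-protocol gap is structural more than numerical. At 95-98% completion and an assumed 70-90% delay in non-completers, comparing completers with all usual-care patients adds 0.5-2.4 points of false benefit and gives total two-sided rejection of 10.0-11.4% at 0.10. A reader might infer serious inflation from the 85% scenario, but the documents do not support that rate for modified ITT patients, who have already had surgery at the centre and are expected to attend almost without exception.

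The regression is overloaded under either reading (0.6-1.0 or 1.5-2.0 events per listed item, if all are entered), and its list includes dates that help determine the outcome.

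This should be corrected before analysis. Confidence is medium, because the wording allows more than one reading.

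**What to change.** 1. **Section 9.3.** State that modified ITT is the only between-arm efficacy comparison. Report three-session completers descriptively (PORT delay rate with 95% CI), and label any contrast with usual care non-randomized and supportive. Alternatively, define the per-protocol set by a Visit 2-4 attendance rule recorded in the same way in both arms.
2. **Sections 8.1 and 9.4.3.2.** Either state how and by whom barriers are logged in usual care and name the between-arm test, or label the navigator-log endpoints NDURE-only and descriptive. In the second case, answer the objective with the between-arm change in the number of barriers answered yes on the Perceived Barriers Questionnaire, Visit 1 to Visit 5, by the rank sum test already planned. Because Visit 5 falls at PORT start, repeat with Visit 4 as a sensitivity analysis.
3. **Barrier regression.** Label it exploratory, state which arms it uses, and replace the section 8.1 list with a short pre-specified set without treatment dates, for example nomogram risk and the two stratification factors. With unresolved barriers that is four terms: 18.75/4 to 33.75/4, or about 5-8 events per term in NDURE alone.

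The cost is wording, since the questionnaire is already scheduled; usual-care logging, if chosen, would add data collection. Downsides:
- The descriptive option gives up a between-arm per-protocol efficacy estimate.
- Self-report measures perceived presence of barriers, not confirmed resolution, and would serve two objectives.
- Navigators elicit barriers in the NDURE arm only, which may shift self-report there.
- Patients who have not started PORT may lack a Visit 5 value.
- Events per term stay modest.

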9.4 STATISTICAL ANALYSES

9.4.1 GENERAL APPROACH

We will construct graphical displays and calculate descriptive statistics (e.g. frequencies and percent for categorical variables, and mean, median, standard deviation, and range for continuous variables). Covariates will be specified below. For inferential tests, we will use a p-value of 0.05, two-sided, and 95% confidence intervals (CIs) to assess statistical significance (Type I error). Covariates will be pre-specified as described below. Normality of the data will be assessed before underlying statistical procedures will be performed. We will evaluate variable transformations as needed to satisfy assumptions and consider transformations of variables to induce approximate normality and stabilize variance as needed. Nonparametric tests will be applied when appropriate.

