4.2 RCT OF NDURE VERSUS USUAL CARE

4.2.1 OVERALL DESIGN

We will conduct a single-site, non-blinded, parallel-group, RCT of NDURE versus usual care for the management of delays and racial disparities starting PORT in adults with surgically-managed, locally advanced HNSCC. The study is designed to test the following hypotheses: 1) NDURE will result in a lower rate of delayed PORT relative to usual care (primary objective) and 2) NDURE will result in a smaller difference in PORT delay between AA and whites relative to usual care (secondary objective). The statistical plan for this between-group design analyzes the superiority of NDURE relative to usual care, although our power analysis is calculated with $\alpha = 0.1$ and $1 - \beta = 0.8$ based on the desire to emphasize power over type I error at this early stage of development (single-site pilot RCT) to ensure follow-up on promising interventions.

Upon enrollment and completion of the baseline assessments, patients will be randomized 1:1 to NDURE or usual care using a permuted block randomization method, with randomly selected block sizes of 2 or 4. Randomization, which will occur at the individual patient level, will be stratified with a 1:1 allocation ratio with strata defined by race (white, AA) and location of radiation facility (MUSC, non-MUSC) because of the known association of these variables with PORT delay^{6,33}. Furthermore, to facilitate evaluation of PORT delay rates in racial subgroups, we will oversample AAs for a final sample size of 50 white and 25 AA patients in each arm (see details in **Section 9.4.6, Sub-Group Analyses**). Given the impossibility of delivering the NDURE intervention in a non-blinded fashion, allocation concealment will be non-blinded. The study statistician ([name]) will generate the randomization schema and

randomization list. The study coordinator will implement the randomization. Randomization errors will be handled as per the modified intention-to-treat (ITT) population for the efficacy analysis.

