9.2.2 RCT OF NDURE VERSUS USUAL CARE

Power and sample size calculations were performed using PASS v08.0.13, “Inequality Tests for Two Independent Proportions.” The primary endpoint for this pilot RCT is the rate of PORT delay, defined as starting PORT > 6 weeks after surgery. Our primary objective is to compare PORT delay rates between the NDURE and usual care arms. We hypothesize that, compared with patients who receive usual care, patients who receive NDURE will have a decreased rate of PORT delay (initiation of PORT > 6 weeks after surgery). Alternatively, our null hypothesis is that there will be no difference in the rate of PORT delay between NDURE and usual care. We assume the rate of PORT delay in the usual care arm will be 45%³³ and target an absolute reduction in PORT delay of 20% (rate of PORT delay in the NDURE arm = 25%)²⁴. This effect size is clinically significant and realistic given results in similar (non-randomized) interventions²⁴. Seventy-five patients in each arm yields 83% power to detect a 20% reduction in PORT delay (45% versus 25%) based on a two-sided Mantel-Haenszel test of two independent proportions assuming a two-sided $\alpha = 0.1$. Our choice of the Mantel-Haenszel test to compare proportions is based on the trial’s stratified design. Our selection of $\alpha = 0.1$ and $1 - \beta = 0.8$ is based on the desire to emphasize power over type I error at this early stage of development (single-site pilot RCT) to ensure follow-up on promising interventions. We therefore consider our RCT to be appropriately and rigorously designed to detect a clinically meaningful reduction in PORT delay. In order to have 150 patients eligible for the

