9.4.2.2 RCT OF NDURE VERSUS USUAL CARE

For the primary endpoint (delays starting PORT as defined in **Section 8.1, Endpoint and Other Non-Safety Assessments**), we will calculate the percentage of patients who start PORT > 6 weeks after surgery and corresponding 95% confidence interval (CI) for both arms and for white and AA subgroups within each arm in the efficacy analysis population. The rate of PORT delay will be compared between arms using a Mantel-Haenszel test of two proportions, with strata defined by race and location of radiation facility.

Every effort will be made to minimize missing data and lost-to-follow-up participants. Participants will complete assessments at baseline and post intervention using an iPad-based REDCap collection method. The program coordinator will attempt to contact patients at least three times using a variety of methods of communication (e.g. text message, phone call, email, mail, etc) to complete outcome measures. This method resulted in 100% instrument completion in prior studies conducted by our team.

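### The RCT is sized at two-sided alpha 0.10 but the analysis section tests at two-sided 0.05, so the stated 83% power is about 73% for the analysis as written.

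*Combined protocol and SAP*

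**What the plan says.** Four places in the combined protocol and SAP bear on the level of the primary test.

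- **Section 4.2.1 (Overall Design)** describes a superiority comparison and adds that "our power analysis is calculated with $\alpha = 0.1$ and $1 - \beta = 0.8$ based on the desire to emphasize power over type I error". It does not say whether this level is one- or two-sided.
- **Section 9.2.2 (sample size for the RCT)** states: "Seventy-five patients in each arm yields 83% power to detect a 20% reduction in PORT delay (45% versus 25"%). The calculation uses a two-sided Mantel-Haenszel test at a two-sided alpha of 0.1. The reason given for that level is the same as in Section 4.2.1.
- **Section 9.4.1 (General Approach)** states: "For inferential tests, we will use a p-value of 0.05, two-sided, and 95% confidence intervals (CIs) to assess statistical significance (Type I error").
- **Section 9.4.2.2 (primary analysis of the RCT)** states: "The rate of PORT delay will be compared between arms using a Mantel-Haenszel test of two proportions", stratified by race and radiation facility. It gives no significance level. The 95% intervals it plans are for the delay rate within each arm and subgroup, not for the difference between arms.

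Nowhere does the document say that the primary comparison is judged at 0.10.

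**The concern.** Power is a property of a test at a stated level. The 83% belongs to a test at two-sided 0.10. The only level the analysis section gives is two-sided 0.05, and nothing exempts the primary endpoint from it. As written, the trial does not have the power it claims.

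The decision on the primary endpoint is also left open. For a primary p-value between 0.05 and 0.10, the design rationale points to a promising result worth following up, while Section 9.4.1 makes it non-significant. The trial is not blinded (Section 4.2.1), and the principal investigator reviews endpoint data monthly (Section 10.1.6). A level chosen after results are visible would not be credible.

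**Working it through.** **Inputs.** All are from Section 9.2.2 except the second alpha, which is from Section 9.4.1: n = 75 per arm; p₁ = 0.45 (usual care); p₂ = 0.25 (NDURE); difference 0.20; alpha 0.10 or 0.05, both two-sided. The 150 patients are the analysable modified ITT population, so the planned enrolment of 170 does not alter these figures.

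**Formula.** Normal approximation with pooled variance under the null and no continuity correction:

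Power = Φ[(0.20 − z × SE₀) / SE₁]

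- Mean rate = (0.45 + 0.25)/2 = 0.35
- SE₀ = √(2 × 0.35 × 0.65 / 75) = 0.0779
- SE₁ = √((0.45 × 0.55 + 0.25 × 0.75) / 75) = √(0.435/75) = 0.0762

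**Step 1: reproduce the stated figure (alpha 0.10, z = 1.645).** (0.20 − 1.645 × 0.0779)/0.0762 = 0.944, and Φ(0.944) = **82.7%**. The stated 83% reproduces.

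**Step 2: apply the level in Section 9.4.1 (alpha 0.05, z = 1.960).** (0.20 − 1.960 × 0.0779)/0.0762 = 0.622, and Φ(0.622) = **73.3%**. The chance of missing the effect goes from 17.3% to 26.7%.

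**Step 3: check that the gap does not depend on the method.**

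| Method | Alpha 0.10 | Alpha 0.05 |
|---|---|---|
| Pooled normal approximation | 82.7% | 73.3% |
| Unpooled normal approximation | 83.7% | 74.7% |
| Exact enumeration, unstratified Mantel-Haenszel | 83.3% | 73.5% |
| Simulated four-stratum Mantel-Haenszel, equal rates in all strata | 83.2% | 73.5% |
| Simulated four-stratum Mantel-Haenszel, one set of unequal rates | 85.2% | 76.4% |
| Pooled, continuity-corrected | 77.9% | 67.2% |

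The simulations use 200,000 runs and strata of 25, 25, 13 and 12 per arm. That takes the planned 50 white and 25 AA patients per arm and assumes a roughly even facility split, which the document does not give. The unequal stratum rates are also assumed: 33%, 48%, 48% and 63% under usual care against 16%, 26%, 26% and 41% under NDURE. Every method loses about 9 to 11 points. The continuity-corrected version does not reproduce the stated 83%.

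**Step 4: sample size needed at alpha 0.05.** n per arm = [1.960 × √(2 × 0.35 × 0.65) + z_power × √0.435]² / 0.20².

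- 80% power (z = 0.842): (1.322 + 0.555)²/0.04 = 88.1, so **89 per arm** (178 analysable)
- 83% power (z = 0.954): (1.322 + 0.629)²/0.04 = 95.2, so **96 per arm** (192 analysable)

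**Step 5: how often the two rules disagree.** Under the design assumptions, exact enumeration gives 83.26% − 73.54% = **9.7%** probability of a p-value between 0.05 and 0.10. For example, 34/75 against 23/75 delayed (45.3% against 30.7%, a difference of 14.7 points) gives an unstratified Mantel-Haenszel p of about 0.065.

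**The case against.** The strongest reply is that the two levels serve different purposes. Section 4.2.1 attaches 0.1 to the power analysis, and Section 9.2.2 does the same. Neither states a success criterion. On that reading the sizing was deliberately lenient and inference is at 0.05. This does not rescue the plan: it means that the 83% describes a test nobody intends to run.

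The opposite reply is that 0.10, justified twice and specific to the RCT, overrides a general section that also covers the feasibility study. That may well be what was intended, but the text does not say so, and Section 9.4.2.2, the natural place for an override, is silent.

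A third reply is that this is a pilot. The document contains no formal go/no-go rule, and Section 4.2.2 presents the RCT partly as a source of effect and sample-size estimates for a phase III trial. That stands, and it limits the harm: the verdict changes only if p lies between 0.05 and 0.10. Even so, Section 9.1 states a null and an alternative hypothesis for the primary endpoint, and Section 9.2.2 defends the design on its ability to detect the target reduction.

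Two smaller points also stand. The 83% is not a miscalculation, since it is right for the level it assumes. The stratified simulation figures rest on assumptions outside the document, so the finding relies on the unstratified calculation.

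**Conclusion.** The concern holds. The significance level used for sizing and the level prescribed for analysis differ, with nothing to reconcile them for the primary endpoint. With 75 analysable patients per arm and true rates of 45% and 25%, power is about 83% at two-sided 0.10 and about 73% at two-sided 0.05. The lower figure is roughly 9 points down and below the 80% target in Sections 4.2.1 and 9.2.2. It assumes the protocol's own delay rates and an uncorrected test, which is the form that reproduces the stated power. The document does not settle which level was meant. It needs correcting because it concerns the decision rule for the primary test.

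**What to change.** Choose one level for the primary test, and date the decision before any between-arm outcome comparison is seen.

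- **Preferred, as it follows the stated design rationale:** say in Sections 9.4.1 and 9.4.2.2 that the primary Mantel-Haenszel test is judged at two-sided alpha 0.10, and add a 90% confidence interval for the between-arm difference as the matching interval. Keep 0.05 and 95% intervals for secondary and descriptive results. The 83% then stands.
- **If 0.05 is intended:** restate the power in Section 9.2.2 as about 73%, and correct the alpha and 80% power statements in Sections 4.2.1 and 9.2.2.
- **If 0.05 and 80% power are both wanted:** resize to 89 analysable patients per arm.

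The first two options need only a few sentences and no extra patients. Their price is openly labelling the primary test as 10% two-sided, or quoting a less favourable power. The third adds 178 − 150 = 28 analysable patients. Keeping the planned one-third AA share would then require 178/3 ≈ 59 AA patients, against the 50 expected in 36 months, or 96 × 0.60 ≈ 58 in the extended 42 months.
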